5.1.1 Study duration per subject

Subject recruitment for the study will begin in approximately Q2 2011. For each subject, the study will last from study entry until either regulatory approval of BRV has been granted by any Health Authority in an indication of adjunctive treatment of POS, until the Sponsor decides to close the study; until subjects transition to another BRV study; until a managed access program, named patient program, compassionate use program, or similar type of access program is established as allowed per country-specific requirement in addition to legal and regulatory guidelines; or until BRV development is stopped by the Sponsor.

The following study periods are defined:

- Evaluation Period (Visit 1 until the Last Evaluation Period Visit or Early Discontinuation Visit [EDV]): Subjects who enroll in N01379 will immediately enter the Evaluation Period.
- Down-Titration Period (up to 4 weeks)
 - If the subject is discontinuing study drug, the Investigator will first plan an EDV followed by the progressive down-titration of study drug.
 - During the Down-Titration Period, the BRV dose may be decreased in steps of a maximum of 50mg/day on a weekly basis. A last down-titration step at 20mg/day for 1 week should be included prior to the Posttreatment Period.
- Posttreatment Period (2 to 4 weeks): After completion of the Down-Titration Period, or for those subjects who for extenuating circumstances do not complete a Down-Titration Period, the subject will be required to enter a Posttreatment Period for a minimum of 2 weeks and a maximum of 4 weeks, followed by a Final Visit (FV).
- The end of the study is defined as the date of the last visit of the last subject in the study.

For subjects who transition to another BRV study or a managed access program or similar type of program or who will be converted to commercial BRV if, when, and where available, the Down-Titration Period and FV are not applicable.

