3 DATA ANALYSIS CONSIDERATIONS

3.1 General presentation of summaries and analyses

Statistical analysis and generation of tables, figures, subject data listings, and statistical output will be carried out using SAS® Version 9.1 or higher.

Descriptive statistics, such as the mean, standard deviation (SD), median, 25th percentile, 75th percentile, minimum value, and maximum value for quantitative variables, and counts and percentages for categorical variables, will be provided. Denominators for percentages will generally be based on the set of subjects with at least 1 assessment at the time point or at least 1 assessment during the time interval being summarized.

All summaries will be descriptive; no statistical hypothesis testing is planned.

Unless otherwise noted, summaries will present BRV overall, which will include all subjects exposed to BRV during the study.

Subject data listings will be provided and will present source data and key derived variables for statistical analyses.

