3.2.4 Study periods

The Baseline Period for N01379 corresponds to the Baseline Period of the previous studies, and is defined for seizure outcomes and direct cost parameters. The Baseline Period is defined as study days on or after the date of Visit 1 and prior to the date of Visit 2 for N01258 and study days on or after the date of Visit 1 and prior to the date of Visit 3 for N01358.

The study is divided into 3 periods: Evaluation Period, Down-Titration Period, and Post-Treatment Period. A subject is classified as “discontinued” if the subject has a termination case report form (CRF) or has an early discontinuation visit (EDV). A subject is classified as “completed” if this subject completes the full extent of the study as defined in the protocol at database lock.

A “discontinued” subject can be potentially slotted into the 3 periods of the study. The following algorithms will be used to slot the subject appropriately into the Evaluation Period, Down-Titration Period, and Post-Treatment Period.

- For Evaluation Period, the start date is the date of first dose of BRV, and the following algorithm is used to determine the end date:
 - If the subject enters the Down-Titration Period, then the date of EDV is the end date;
 - If the subject does not enter the Down-Titration Period but meets 1 of the following criteria, the Evaluation Period ends on date of last dose of BRV:
 - Without an EDV but having a termination CRF,
 - With an EDV and having a termination CRF,
 - With an EDV and the date of EDV prior to the database lock date and having no termination CRF.

- A subject is considered entering Down-Titration Period only if the subject has an EDV and at least 1 dose of study drug after the date of EDV, the start date of Down-Titration Period is set as 1 day after the date of EDV, and the Down-Titration Period ends on date of last dose of BRV. A subject without an EDV but having a termination CRF or with an EDV but without any dosing of study drug after the EDV will not have the Down-Titration Period, and no artificial Down-Titration Period will be created for analysis.
- A subject is considered entering the Post-Treatment Period if the subject has at least 1 contact (scheduled visit, unscheduled visit, or telephone contact) after the date of last dose of BRV. The Post-Treatment Period starts 1 day after date of last dose of BRV irrespective of entering the Down-Titration Period, and there is no end date.

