11.1 Extent of exposure

A daily dose will be calculated for each study day from the day of first dose of BRV to the day of last dose of BRV for the purposes of calculating modal dose. Daily dose will be calculated as the sum of the AM and PM dose for each day.

Modal daily doses will be calculated across all study days on or after the day of first dose of BRV and up to and including the day of last dose of BRV. Modal daily dose is the most frequently taken daily dose during this period. In the event of a tie, the modal dose will be set to the lower of the tied doses. Modal daily dose will be categorized as follows:

Category	Definition
5 mg/day	<20mg/day
20mg/day	≥20mg/day to <50mg/day
50mg/day	≥50mg/day to <100mg/day
100mg/day	≥100mg/day to <150mg/day
150mg/day	≥150mg/day to <200mg/day
200mg/day	≥200mg/day

Subject years of exposure will be calculated by summing the exposure duration in days for all subjects being summarized, and dividing the resulting value by 365.25.

Subject years of exposure will be presented overall and by modal dose for the Safety Analysis Set. The subject years of exposure presented by modal dose will be the total subject years of exposure of subjects with that modal dose.

The number and percentage of subjects exposed to BRV will be summarized overall and by modal dose category. The number and percentage of subjects in each Exposure Duration Cohort (≥3 months, ≥6 months, ≥12 months, and so forth) will be summarized.

The number and percentage of subjects within each modal dose category will be summarized for each Exposure Duration Cohort; percentages will be relative to the total number of subjects in each Exposure Duration Cohort.

In addition to the overall summaries of the above, the above will also be summarized by subgroup for region (North America, Europe [EU member states], Europe [non-EU member states], Asia/Pacific/Other), and seizure type (Partial Onset Seizures, Primary Generalized Seizures).

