11.2.2 General summaries of TEAEs

Pre-treatment AEs will be provided in a subject data listing; no summaries of pre treatment AEs are planned.

An overall summary of AEs will provide the overall number of TEAEs and the numbers and percentages of subjects with at least 1 TEAE, with a TEAE that led to permanent discontinuation of study drug, with a drug-related TEAE, with a severe TEAE, with a treatment-emergent SAE, and with a drug-related treatment-emergent SAE. The number and percentage of subjects who died will also be summarized. This summary will be provided for all subjects in the Safety Analysis Set and also by subgroup for geographic region and seizure type.

The following summaries of TEAEs will be provided by MedDRA SOC and PT. All summaries are for the combined Evaluation, Down-Titration, and Post-Treatment Periods unless otherwise indicated.

Overall Incidence Summaries

- Incidence of TEAEs
- Incidence of TEAEs by 3-month time interval
- Incidence of TEAEs by study period (Evaluation, Down-Titration, Post-Treatment)
- Incidence of TEAEs for TEAEs occurring in at least 5% of subjects
- Incidence of TEAEs by 3-month time intervals for TEAEs occurring in at least 5% of subjects overall
- Incidence of non-serious TEAEs occurring in at least 5% of subjects

The incidence of TEAEs occurring in at least 5% of subjects will be summarized overall as noted above and also by subgroup for geographic region, seizure type, and randomized treatment from the previous double-blind study.

A subject is included in a 3-month interval if the subject was receiving BRV at any time during that interval based on their duration of exposure to BRV (eg, a subject with exposure for 91 days is included in the time interval for Months 1-3 and Months 4-6). Summaries of AEs by 3-month intervals will include all subjects who are classified into each time interval as defined above. TEAEs which had onset prior to or on the date of the last dose of BRV) are included in summaries by 3-month time intervals.

Maximum Intensity and Causality

- Incidence of TEAEs by maximum intensity
- Incidence of drug-related TEAEs

Serious Adverse Events

- Incidence of treatment-emergent SAEs

Discontinuations due to TEAE

- Incidence of TEAEs leading to permanent discontinuation of study drug

TEAEs of interest

AEs of interest will be identified based on MedDRA search criteria, which are documented outside of the SAP. The following summaries will be provided for AEs of interest:

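### The by-period TEAE table gives percentages of subjects with no time denominator, so it cannot show whether events become more frequent during down-titration

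*SAP*

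**What the plan says.** SAP 11.2.2 lists, among the overall incidence summaries, "Incidence of TEAEs by study period (Evaluation, Down-Titration, Post-Treatment"). SAP 3.1 sets the metric: "counts and percentages for categorical variables, will be provided". It also says "All summaries will be descriptive; no statistical hypothesis testing is planned". No denominator is defined for the by-period table beyond the general rule in SAP 3.1: "Denominators for percentages will generally be based on the set of subjects with at least 1 assessment at the time point", or during the interval being summarised.

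The periods differ greatly in length:

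- **Evaluation** has no fixed length. It starts at first dose and ends at the Early Discontinuation Visit, or at last dose for a discontinued subject who does not taper (SAP 3.2.4). SAP 5.1 plans retention estimates out to 60 months.
- **Down-Titration** is, in Protocol 5.1.1, "Down-Titration Period (up to 4 weeks"). SAP 3.2.4 defines it by dates alone and sets no cap: "the Down-Titration Period ends on date of last dose of BRV".
- **Post-Treatment** starts the day after last dose and has no end date in SAP 3.2.4.

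Person-time is planned only as an exposure summary (SAP 11.1): "Subject years of exposure will be presented overall and by modal dose for the Safety Analysis Set". It is not split by period and is not used as a denominator for TEAEs. No exposure-adjusted TEAE rate is defined anywhere in the SAP.

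**The concern.** The percentage of subjects with at least one event rises with observation time even when the underlying rate is constant. A column covering a year or more, set beside one covering at most a few weeks, will show a far higher percentage in the longer period almost regardless of what the drug or its withdrawal does. A reader looking for an effect of reducing BRV would see a small taper column and could take it as reassurance.

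Occurrence of a TEAE is a primary safety variable (Protocol 4.1.1). The protocol makes a phone call at the end of down-titration mandatory, and Protocol 8.7 lists AE recording as its only procedure, so the taper data are collected on purpose. Clinically significant worsening of seizures is recorded as an AE (Protocol 10.1.1), and no planned seizure summary isolates the taper. Among the planned TEAE summaries, the by-period table is the only one with a separate taper column.

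The denominator adds to the problem. Subjects who convert to commercial BRV or move to an access programme do not taper (Protocol 5.1.1), so those who taper are a subset. The SAP does not say that the Down-Titration column uses that subset.

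**Working it through.** **Plan's own figure.** There is none to reproduce: no event rate, expected Evaluation length or between-period ratio is stated. One side check is possible. Protocol 5.1.1 says "the BRV dose may be decreased in steps of a maximum of 50mg/day on a weekly basis", with a last week at 20 mg/day. From 200 mg/day that gives 150, 100, 50 and 20, which is four weekly steps and agrees with the planned 4 weeks.

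**Model (assumed, not in the documents).** Constant hazard L per year for a first TEAE in Evaluation of length T years. The hazard doubles to 2L in a taper of 4/52 year.

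- Evaluation percentage = 1 − exp(−L·T)
- Taper percentage = 1 − exp(−2L·4/52)
- Apparent ratio = Evaluation percentage ÷ taper percentage

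**One year of Evaluation.**

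| L per year | Evaluation | Taper (rate doubled) | Ratio |
|---|---|---|---|
| 0.1 | 9.5% | 1.5% | 6.2 |
| 0.5 | 39.3% | 7.4% | 5.3 |
| 1 | 63.2% | 14.3% | 4.4 |
| 2 | 86.5% | 26.5% | 3.3 |

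**Ratio over a wider range of assumptions.**

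| L per year | T = 0.25 y | 0.5 y | 1 y | 2 y | 5 y |
|---|---|---|---|---|---|
| 0.05 | 1.6 | 3.2 | 6.4 | 12.4 | 28.9 |
| 0.1 | 1.6 | 3.2 | 6.2 | 11.9 | 25.8 |
| 0.5 | 1.6 | 3.0 | 5.3 | 8.5 | 12.4 |
| 1 | 1.5 | 2.8 | 4.4 | 6.1 | 7.0 |
| 2 | 1.5 | 2.4 | 3.3 | 3.7 | 3.8 |

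**Break-even.** The two percentages are equal when L·T = 2L·4/52, that is T = 8/52 year or 8 weeks, whatever L is. Below 8 weeks of Evaluation the doubled rate shows as a higher taper percentage; above it, as a lower one.

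**Sensitivity.**

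- *Shorter taper* (L = 0.5, T = 1): the ratio is 7.0 for 3 weeks and 10.4 for 2 weeks.
- *Variable Evaluation length* (exponential, mean 1 year): the Evaluation percentage becomes L/(1 + L). The ratio is 6.0, 4.5, 3.5 and 2.5 for L = 0.1, 0.5, 1 and 2.
- *Denominator* (L = 0.5, T = 1): if the whole Safety Population were used and half of it tapered, 7.4% becomes 3.7% and the ratio 5.3 becomes 10.6.

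**With a time denominator.** First events divided by time at risk estimate L and 2L, so the doubling appears as 2.0 by construction. Comparing the taper with a 4-week Evaluation window gives 1.99, 1.96, 1.93 and 1.86 for L = 0.1, 0.5, 1 and 2. Either form points the right way.

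The time must be matched to the count. Take L = 0.5, T = 1 and *no* change in rate. Subjects with an event over *all* period time give 39.3 per 100 subject-years in Evaluation. In the taper, 1 − exp(−0.5·4/52) = 3.77%, and 3.77/0.0769 = 49.0 per 100. That is a spurious ratio of 49.0/39.3 = 1.25.

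**Whether the 3-month tables fill the gap.** SAP 3.2.5 anchors those intervals on first dose, and SAP 11.2.2 includes events up to last dose. A taper event falls into whichever interval it occurs in, pooled with subjects still in Evaluation. These tables handle unequal time on treatment but do not isolate the taper.

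**The case against.** The table is descriptive, and no objective concerns withdrawal or a contrast between periods. The protocol states the taper length, so an informed reader can allow for it. Listings with source data and relative day are planned (SAP 3.1, 3.2.2), so individual taper events stay visible, and ongoing safety review is in place (Protocol 10.1.8, 12.8). Taper rates would rest on little person-time.

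Part of this stands. The SAP tabulates the periods side by side; a reader might infer a planned comparison, but none is specified. A reader might also infer that the date rule in SAP 3.2.4 is itself wrong. It is a workable definition, and the difficulty lies in how SAP 11.2.2 uses it. Nor is Down-Titration the only place where withdrawal effects could appear. With a half-life of about 8 hours (Protocol 2.2), some may arise after last dose, and subjects who stop without tapering go straight to Post-Treatment.

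None of this supplies what is missing. Knowing the taper lasts about 4 weeks does not let a reader turn a percentage into a rate when Evaluation time is not shown by period. Listings and safety review are not summaries of frequency.

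**Conclusion.** The point holds as a limitation of one planned table. Percentages over periods of very different length, with no person-time, cannot show whether TEAEs become more frequent during taper. Under a constant hazard, a doubled rate would appear as a lower percentage whenever Evaluation lasts more than about twice the taper (8 weeks against 4).

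The size is illustrative. At 1 year of Evaluation and 0.1 to 2 first TEAEs per year the doubled rate looks about 3 to 6 times lower; over the wider ranges tried, about 1.5 to 29 times. A reader might settle on a single figure such as five times. The documents do not support one: they give neither the rate nor the Evaluation length. A ratio of 5 needs Evaluation of roughly 0.8 to 1.25 years at 0.1 to 1 event per year. At 1.5 per year or more it cannot be reached at any length, since the ceiling 1/[1 − exp(−2L·4/52)] is 4.9 at L = 1.5 and 3.8 at L = 2.

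The constant hazard is also an assumption. The direction of the distortion needs only that Evaluation be much longer than the taper.

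**What to change.** In SAP 11.2.2, for the by-period table:

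1. State that the denominator of each column is the subjects who entered that period under SAP 3.2.4.
2. Add subject-years and TEAE rates per 100 subject-years for Evaluation and Down-Titration, overall and by SOC and PT. Use either first events over time to first event in the period, or all events over all period time, and say which.
3. State that the SAP 3.2.4 period dates also apply to completed subjects. The explicit start and end rules are written for discontinued subjects only.
4. Leave Post-Treatment as percentages unless an end date is set for its person-time.
5. If the Evaluation rate is also shown for subjects who tapered, note that AEs leading to discontinuation fall in Evaluation by construction. They inflate that rate and could hide a rise in taper. Alternatively, show it with and without those events.

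The cost is SAP wording and a few columns in one table, using dates already needed for the periods; no new data are collected. The downside is imprecision: every 100 subjects who complete a full 4-week taper contribute at most 100 × 4/52 = 7.7 subject-years, so rates for single preferred terms will be unstable and should be read with their counts.

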3.2.5 Monthly time intervals

A month is defined as 30 days and time intervals based on monthly durations are defined as a multiple of 30 days (eg, 12 months is defined as 360 days). The following definitions of 3-month and 6-month intervals are based on 30-day months where the date of first dose of BRV is Day 1:

Interval	Duration Definition
Months 1-3	Days 1-90
Months 4-6	Days 91-180
Months 7-9	Days 181-270
Months 10-12	Days 271-360
Months 1-6	Days 1-180
Months 7-12	Days 181-360
Months 13-18	Days 361-540
Months 19-24	Days 541-720

Subsequent 3- and 6-month intervals are defined in a similar manner.

Six-month intervals are defined for the evaluation of direct and indirect cost parameters.

Statistical summaries for direct and indirect cost parameters will only present results through the first 2 years of treatment. Three-month intervals will be used for analysis of efficacy outcomes and AEs.

For the analysis of efficacy outcomes, a subject is included in the analysis for a 3-month interval if the end date is on or after the *last day* of the 3-month interval and the subject diary was completed for at least 1 day during the 3-month interval.

For the analysis of AEs, a subject is included in the analysis for a 3-month interval if the end date is on or after the *first day* of the 3-month interval.

3.2.6 Last Value on BRV Treatment

Last Value for QOLIE-31-P, HADS, and socio-professional data is the last assessment strictly after the date of first dose of BRV and up to and including the YEV at the end of the second year and any EDVs for subjects who did not complete through the YEV at the end of the second year.

Last Value for clinical laboratory parameters, vital signs, and ECGs is the last available result obtained after the first dose of BRV and prior to or on the date of last dose of BRV. All scheduled and unscheduled assessments within this time period will be considered. Last Value will be determined separately for each laboratory parameter for hematology, chemistry, urinalysis, and endocrinology assessments.

3.2.7 Exposure duration and exposure duration cohorts

At the final analysis, the overall duration of exposure (or On Treatment Period) will be calculated as the date of last dose of BRV minus the date of first dose of BRV plus 1 day.

Each subject will be classified into one or more of the following exposure duration cohorts based on the duration of BRV exposure as calculated above:

All subjects	≥1 day
≥3 months	≥90 days
≥6 months	≥180 days
≥12 months	≥360 days

This categorization will continue in 6-month increments past 12 months up to a time point that will be determined based on cumulative exposure at the time of the database lock.

3.2.8 Study visit cohorts

Study visit cohorts are defined for summaries of QOLIE-31-P and HADS. Six-month, 12-month, 18-month, and 24-month cohorts are defined. Subjects will be classified into a study visit cohort if they attend the scheduled visit at the time point defined by the cohort. For example, subjects will be included in the 18-month study visit cohort if they attend the scheduled visit at 18 months (ie, FEV at Month 18). Subjects may be classified in more than 1 cohort. Generally, subjects included in a cohort for a later visit will be included in all earlier study visit cohorts (eg, 6-month and 12-month study visit cohorts for subjects in the 18-month study visit cohort), although this may not be the case in the event of a missed visit or if an unscheduled visit is conducted in lieu of a scheduled visit.

3.3 Definition of Baseline Values

Baseline for all study outcomes will be based on baseline from the previous studies. For assessments performed at scheduled and unscheduled visits, Baseline will generally be the last result obtained or prior to the randomization visit of the previous study. Baseline will be defined separately for each hematology, blood chemistry, urinalysis, and endocrinology parameter.

Baseline for the evaluation of seizure frequency and seizure days will be calculated from the core study seizure diary based on the rules defined in Section 3.8.1.

3.4 Protocol deviations

The criteria for identifying important protocol deviations and the classification of important protocol deviations will be defined separately in the Specification of Protocol Deviations document. Whenever possible, criteria for identifying important protocol deviations will be implemented algorithmically to ensure consistency in the classification of important protocol deviations across all subjects.

3.5 Analysis populations

3.5.1 Safety Population

The Safety Population will consist of all subjects who took at least 1 dose of study drug.

Summaries of demographics and baseline characteristics, medical history, AEDs, non-AEDs, HADS, study drug exposure, and safety outcomes will be provided for the Safety Population.

3.5.2 Efficacy populations

Efficacy Populations will consist of all subjects who took at least 1 dose of study drug and have at least 1 seizure diary day during the Evaluation Period. Separate Efficacy Populations are defined for subjects with focal epilepsy from N01358 and N01258 and subjects with generalized epilepsy from N01258.

A subject will be excluded from the Efficacy Analysis Set for POS or PGS if either they did not receive at least 1 dose of BRV, or the clinical database indicates that the daily seizure diary was not completed for any days on or after the first dose of BRV and on or prior to the end date of the Evaluation Period (see Section 8). Subjects were assigned to a POS population or a PGS population in the previous study, based on diagnosis or medical history.

Seizure outcomes will be summarized for either the Efficacy Population for POS or the Efficacy Population for PGS. Summaries of epilepsy history and QOLIE-31-P will be provided for the Efficacy Populations for both POS and PGS.

